5.7.1.3. Phase Allocation of Adverse Events

Solicited events are always allocated to the respective Post Dose period.

Step 1: Allocation of events to the periods:

Adverse events in the SDTM data base are allocated to periods based on their start date/time. If the start date/time of an event falls between (or on) the start and stop date/time of a period, the AE is attributed to that period (treatment-emergent principle).

- In case of partial start or stop dates (i.e. time and/or day and/or month and/or year missing), the events are allocated to the periods using the available partial information on start and end date; no imputation will be done. If, for instance, the AE start date only month and year are available, these data are compared to the month and year information of the periods. This rule may lead to multiplication of the event as a consequence of its assignment to multiple periods.

- In case of a completely missing end date, the date is imputed by the cut-off date of the analysis for participants still ongoing in the study, and by the end date of the last period for participants who discontinued or completed the trial. In case of a completely missing start date, the event is

allocated to the first active treatment phase (post dose 1 period), except if the end date of the AE falls before the start of the first active treatment phase (post dose 1 period).

Step 2: Combination of events:

Overlapping/consecutive events are defined as events of the same participant with the same preferred term which have at least 1 day overlap or for which the start date of an event is 1 day after the end date of the preceding event. Overlapping/consecutive events may be combined into one AE or not, according to the following rules:

If overlapping/consecutive events start in one of the following periods - Screening or post dose extension (i.e. non-active periods) - followed by an AE in - post-dose period (active period) - they are allocated to their respective periods and are considered as separate events.

In case overlapping/consecutive events start within a single period, they are considered as one and the same AE. The individual events which contribute to this AE are retained as individual records in the ADaM data base but are assigned the same onset, period, and total duration. All related attributes to the AE/phase/period should also be consistent with the new event.

In case overlapping/consecutive events start in both an active period followed by a non-active period, they are allocated to the active period only and are considered as one and the same AE. The individual events which contribute to this AE are retained as individual records in the ADaM data base but are assigned the same onset, treatment period, and total duration. All related attributes to the AE/phase/period should also be consistent with the new event.

In case an active period is followed by another active period, and the overlapping/consecutive events start in both periods, they are allocated to their respective period and are considered as separate AEs. The same rule applies for 2 non-active periods.

Remarks:

1. Events can only be combined into one and the same AE if their start and stop dates are known.

In case the completely missing end date is imputed (for period allocation), this date is also considered as a complete date.

Time is not considered when determining overlap of events.

5.7.1.4. Missing Data

Missing data will not be imputed. Participants who do not report an event/concomitant medication will be considered as participants without an event/concomitant medication. An AE with a missing severity or relationship will be considered as an AE reported, but will be considered as not reported for the severity or relationship. For example, an AE with missing severity will be considered as an AE reported for the analysis of any grade, but will be considered as not reported for the analysis of at least grade 3.

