Safety analyses will be performed on the FAS. No formal statistical testing of safety data is planned. Safety data by double-blind vaccination group will be analyzed descriptively. Specific safety analyses will be performed on the Safety Subset. All safety analyses will be tabulated by treatment group (active vaccine, placebo) according to the as-treated principle. All safety analyses will be presented overall and by age and comorbidity (with/without) strata. The main age strata for reporting purposes are ≥ 18 to < 60 years of age and ≥ 60 years of age. In addition, safety data will be analyzed by treatment group and participant seropositivity status at screening.

For the double-blind phase, the safety data up to the unblinding date will be presented separately for the Ad26.Cov 2 double-blind group and the placebo double-blind group (Analysis I). Safety data after the unblinding date but before the open label vaccination date are listed separately.

Additionally, safety data will be pooled for all subjects that received Ad26.Cov 2 (in the double blind phase or in the open label phase) from the start of their Ad26.Cov 2 vaccination to the end of the trial (Analysis II): unsolicited AEs up to day 28, SAEs and MAAEs leading to discontinuation during the entire study, MAAEs until 6 months after last vaccination, AEs of special interest and AEs of interest during the entire study. All tables will be presented by phase.

The safety data from subjects that were unblinded and who received a vaccine outside the study will be tabulated separately.

Subjects that took another COVID-19 vaccine before being unblinded are excluded from the safety tables from the moment they received the other vaccine. The safety data from those subjects after they received the other vaccine are listed separately.

Denominator for the percentages is the number of participants in the considered population and phase for a certain regimen (incidence per 100 participants/phase).

Continuous variables will be summarized using the following statistics, as appropriate: number of observations, arithmetic mean (mean), 95% CI for the mean, standard deviation (SD), median, quartiles (Q1 and Q3), minimum and maximum. Frequencies and percentages (one decimal place) will be generated for categorical variables. No formal comparisons between groups will be provided.

Other exploratory or sensitivity analyses may be performed in addition to the analyses described below on an ad-hoc basis.

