5.7.1. Adverse Events

5.7.1.1. Definitions

Solicited AEs are used to assess the reactogenicity of the study vaccine and are predefined local (at the injection site) and systemic events for which the participant is specifically questioned, and which are noted by participants in their diary. Unsolicited AEs are all AEs for which the participant is not specifically questioned.

Solicited AEs shown in the tables are extracted from the investigator assessment pages (CE) of the CRF (Safety Subset). For unsolicited AEs, only the AEs within the 28-day period following the double-blind vaccination will be presented in the safety tables (Safety Subset), except for SAEs, MAAEs leading to study discontinuation and AESIs, which will be captured and tabulated in the outputs covering the whole study period and for all subjects in the FAS, and MAAEs (including new onset of chronic diseases) which will be captured and tabulated in the outputs covering the 6 month post double-blind vaccination period (Phases: Post-dose, Follow-up (D30-M6), and Follow-up (M6-W52)) and for all subjects in the FAS.

Solicited administration site symptoms will be by definition considered as related to the study vaccine.

The severity of the AEs will be classified as grade 1 to 4. Solicited events that are graded less than grade 1, are not considered as AE. In case no grades are available, the grading of the solicited events will occur according to the grading list in [Appendix 6](#).

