5.7.2. Vital Signs

No ECG are measured in this study. For HIV Viral Load and CD4 counts only abnormalities emerging after double-blind vaccination will be tabulated by worst abnormality grade using the following gradings (absolute CD4+ Count: 300 – 400/mm³ (grade 1); 200 – 299/mm³ (grade 2)

100 – 199/mm³ (grade 3) and < 100/mm³ (grade 4) and for viral load when a subject goes from undetectable to detectable HIV RNA copies/mL.

For all participants, weight and height (and BMI) at baseline will be summarized using descriptive statistics. Vital sign abnormalities emerging after double-blind vaccination may be tabulated/listed by worst abnormality grade using the FDA grading table in [Appendix 6](#).

Temperature will be measured at each scheduled time point and summarized using descriptive statistics. A listing of participants with fever will be provided. Other vital signs may be measured at the discretion of the investigator. For those, vital signs abnormalities of at least grade 3 will be listed.

For COVID-19 cases, temperature will be summarized over time from start of symptoms, using descriptive statistics and/or graphically. Temperature and oxygen saturation will be summarized separately for the measures by the participants as well as by the site. For temperature, systolic and diastolic blood pressure, heart rate, respiratory rate, oxygen saturation, and pulse oximetry, values and the percentage of participants with values beyond clinically relevant limits will be summarized at each scheduled time point. Descriptive statistics will be calculated for changes between COVID-19 Day 29 and COVID-19 Day 3-5 for vital signs that were captured by the site. The schedule for COVID-19 cases will start for each participant on Day 1 of a COVID-19 Episode, will be on a daily basis and take the maximum of the values recorded for each subject per day.

An abnormality (toxicity grade or abnormality based on normal ranges) will be considered as emerging in a particular period if it is worse than the baseline value. If the baseline is missing, the abnormality is always considered emerging. A shift from ‘abnormally low’ at baseline to ‘abnormally high’ post baseline (or vice versa) is also emerging. In case a laboratory test result is censored (no numeric value is available, but only a verbatim term) then a numeric value will be imputed by a value exceeding the cut-off value with one unit. (<x: subtract 1 unit from x, >x: add 1 unit to x; <3.45 is imputed with 3.44).

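### The no-report-means-no-event rule also covers solicited AEs, so Safety Subset participants with no solicited data are tabulated as event-free and absolute reactogenicity rates are understated

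*SAP*

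**What the plan says.** SAP section 5.7.1.4 opens with "Missing data will not be imputed" and continues that "Participants who do not report an event/concomitant medication will be considered as participants without an event/concomitant medication". The rule makes no distinction between solicited and unsolicited AEs.

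The general safety text in section 5.7 sets the denominator: "Denominator for the percentages is the number of participants in the considered population and phase for a certain regimen". Section 5.7.1.2 plans one summary, number and percentage with an exact 95% CI, for both kinds of AE. Nothing restricts solicited percentages to participants with solicited data, and Table 5 (Analysis Sets) defines no set of that kind.

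Section 5.7.1.1 describes solicited AEs as predefined events about which the participant is specifically asked and "which are noted by participants in their diary". For the tables, however, "Solicited AEs shown in the tables are extracted from the investigator assessment pages (CE) of the CRF (Safety Subset"). Section 5.8.1 separately summarises the diary data of the Safety Subset, and uses the investigator's worst grading for symptoms. It states no rule for an absent diary.

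Section 3.4 gives the Safety Subset as about 6,000 participants, about 3,000 per arm. Section 5.7 plans no formal testing of safety data.

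**The concern.** Reading silence as no event is usual for AEs that participants raise themselves. It does not suit solicited AEs. There, a participant who was asked and had no symptom leaves a negative answer, while one with no record at all was not assessed. Scoring the second as the first is single imputation of a favourable value, which sits badly with the opening sentence of the same section.

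Elsewhere the SAP does use the number with data as the denominator. Section 5.5.4.3 reports seroconversion among subjects with an available measurement, and section 5.8.2.6 reports variants among subjects with sequencing data.

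What is at stake is the absolute rate of each solicited reaction. Reactogenicity in the subset is a stated secondary safety objective (section 1.1). The planned CI reflects sampling error only, so it gives no sign of the understatement.

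**Working it through.** The SAP states no solicited AE rate and no completion rate, so there is no figure of its own to reproduce. The following is an illustration.

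**Inputs**
- N = 3,000 per arm (section 3.4).
- p, the true solicited rate: assumed 2%, 20% or 50%.
- m, the share of the Safety Subset with neither diary nor investigator solicited data: assumed 2% to 20%.
- Absence of data is assumed unrelated to the event.

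**Formula.** Events counted = N(1 - m)p. The SAP denominator is N, so the reported rate is p(1 - m). With the denominator limited to participants with data, N(1 - m), the rate is p.

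**Worked case, p = 50%, m = 5%.** Participants with data: 3,000 × 0.95 = 2,850. Events: 2,850 × 0.50 = 1,425. SAP rule: 1,425/3,000 = 47.5%. Restricted denominator: 1,425/2,850 = 50.0%.

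| p | m | SAP rule (exact 95% CI) | Denominator with data (exact 95% CI) |
|---|---|---|---|
| 50% | 2% | 49.0% (47.20 to 50.81) | 50.0% (48.18 to 51.82) |
| 50% | 5% | 47.5% (45.70 to 49.31) | 50.0% (48.15 to 51.85) |
| 50% | 10% | 45.0% (43.21 to 46.80) | 50.0% (48.10 to 51.90) |
| 50% | 20% | 40.0% (38.24 to 41.78) | 50.0% (47.98 to 52.02) |
| 20% | 5% | 19.0% (17.61 to 20.45) | 20.0% (18.55 to 21.52) |
| 20% | 10% | 18.0% (16.64 to 19.42) | 20.0% (18.51 to 21.56) |
| 2% | 10% | 1.8% (1.36 to 2.34) | 2.0% (1.51 to 2.60) |

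Among the values tried, the CI under the SAP rule excludes the true rate from m = 5% when p = 50%, and from m = 10% when p = 20%. At p = 2% it still covers the true rate at m = 20% (1.60%, 1.18 to 2.12).

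**Between-arm contrast**, assumed 50% active against 20% placebo (true difference 30.0 points, true risk ratio 2.50):

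| m active | m placebo | Difference | Risk ratio |
|---|---|---|---|
| 5% | 5% | 47.5 - 19.0 = 28.5 | 2.50 |
| 10% | 10% | 45.0 - 18.0 = 27.0 | 2.50 |
| 10% | 2% | 45.0 - 19.6 = 25.4 | 2.30 |
| 2% | 10% | 49.0 - 18.0 = 31.0 | 2.72 |

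With equal m the difference is multiplied by (1 - m) and the ratio stays the same. With unequal m the difference moves in either direction.

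**The case against.** The strongest objection concerns the data source. The tabulated solicited AEs come from the investigator pages, so a lost diary does not by itself turn a participant into a non-event. That stands, and it is why m is defined here as no solicited data from either source. This fraction cannot exceed the share with no diary and may be much smaller. A reader might infer that each solicited rate falls by the share of missing diaries; section 5.7.1.1 does not support that.

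Three other stronger readings are tempting and also fail.
- Section 5.7.1.4 says an AE of missing severity "but will be considered as not reported for the analysis of at least grade 3", which might suggest that severe solicited reactions are lost. But section 5.7.1.1 grades solicited events without a grade from the Appendix 6 list, so that clause mainly concerns unsolicited AEs.
- In section 5.7.2, "If the baseline is missing, the abnormality is always considered emerging" might look like the opposite convention for the same problem. It concerns a missing baseline when a later abnormality was observed, not a participant with no record.
- It might seem that the vaccine-placebo difference must shrink. That is assured only with equal m in both arms.

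It can also be said that the sizes are hypothetical, that no decision in the plan depends on these tables, and that restricting the denominator has its own bias: if those without data are mostly symptom-free, it overstates the rate. All of this stands and keeps the point minor. It does not remove the rule, which is written and would be applied as it reads.

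**Conclusion.** The point holds as a minor correction. Taken together, sections 5.7.1.4 and 5.7 tabulate a Safety Subset participant with no solicited data from any source as free of every solicited reaction. The absolute rate in each arm is then understated by the relative fraction m, provided absence of data is unrelated to the event. At an assumed 50% rate this is 2.5 points at m = 5% and 5.0 points at m = 10%.

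The SAP fixes neither p nor m, so whether the bias is material cannot be settled from the document. Without any assumption about the non-reporters, the rate in the full subset lies between p(1 - m) and p(1 - m) + m, with p now the rate among those with data. At p = 50% and m = 5% that is 47.5% to 52.5%. The SAP rule reports the lower end of this range as the estimate. Efficacy conclusions are untouched.

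**What to change.** In section 5.7.1.4:
1. Limit the rule that no report means no event to unsolicited AEs and concomitant medication.
2. Base solicited AE percentages on Safety Subset participants with at least one post-vaccination solicited assessment, in the diary or on the investigator pages.
3. Report by arm the number of Safety Subset participants without such data. If it is near zero, the table shows that the choice does not matter.
4. Optionally keep the all-participant denominator as a supporting table, which covers the case where non-reporters are mostly symptom-free.
5. Cross-refer to the Appendix 6 grading fallback in section 5.7.1.1, so that the missing-severity clause is not applied to solicited events that can be graded.

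A further table counting AEs of unknown severity or relationship as grade 3 or related is an optional extra and not part of this correction.

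The cost is one SAP paragraph, a denominator flag and one count per arm. Where m is above zero, reported solicited rates rise somewhat. No study procedure changes.

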5.7.2. Vital Signs

No ECG are measured in this study. For HIV Viral Load and CD4 counts only abnormalities emerging after double-blind vaccination will be tabulated by worst abnormality grade using the following gradings (absolute CD4+ Count: 300 – 400/mm³ (grade 1); 200 – 299/mm³ (grade 2)

100 – 199/mm³ (grade 3) and < 100/mm³ (grade 4) and for viral load when a subject goes from undetectable to detectable HIV RNA copies/mL.

For all participants, weight and height (and BMI) at baseline will be summarized using descriptive statistics. Vital sign abnormalities emerging after double-blind vaccination may be tabulated/listed by worst abnormality grade using the FDA grading table in [Appendix 6](#).

Temperature will be measured at each scheduled time point and summarized using descriptive statistics. A listing of participants with fever will be provided. Other vital signs may be measured at the discretion of the investigator. For those, vital signs abnormalities of at least grade 3 will be listed.

For COVID-19 cases, temperature will be summarized over time from start of symptoms, using descriptive statistics and/or graphically. Temperature and oxygen saturation will be summarized separately for the measures by the participants as well as by the site. For temperature, systolic and diastolic blood pressure, heart rate, respiratory rate, oxygen saturation, and pulse oximetry, values and the percentage of participants with values beyond clinically relevant limits will be summarized at each scheduled time point. Descriptive statistics will be calculated for changes between COVID-19 Day 29 and COVID-19 Day 3-5 for vital signs that were captured by the site. The schedule for COVID-19 cases will start for each participant on Day 1 of a COVID-19 Episode, will be on a daily basis and take the maximum of the values recorded for each subject per day.

An abnormality (toxicity grade or abnormality based on normal ranges) will be considered as emerging in a particular period if it is worse than the baseline value. If the baseline is missing, the abnormality is always considered emerging. A shift from ‘abnormally low’ at baseline to ‘abnormally high’ post baseline (or vice versa) is also emerging. In case a laboratory test result is censored (no numeric value is available, but only a verbatim term) then a numeric value will be imputed by a value exceeding the cut-off value with one unit. (<x: subtract 1 unit from x, >x: add 1 unit to x; <3.45 is imputed with 3.44).

Note: as the grading scale for some parameters in the grading table has some gaps (zones where no toxicity grade definition exists), results falling in these zones will be allocated to the adjacent worst-case grade (cf Appendix 9 of the CTP).

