5.2.1. Identification of COVID-19 cases for adjudication

All COVID-19 episodes and/or SARS-cov-2 infections since the start of the study will be identified using a programmed algorithm described in the section 5.2.2. All fatalities that occur within the study for which COVID-19 could be a contributory or the underlying cause of death will be sent for adjudication, including fatalities not identified by the programmed algorithm. In

addition, cases may be flagged for adjudication through the use of other sources such as the Global Medical Safety database.

All cases identified by the algorithm as severe/critical (tier I)^a or mild (tier V)^a will be sent for adjudication for review on a case by cases basis.

Similarly, moderate cases identified by the algorithm will be sent for adjudication when they have at least one flag=Y for (tier II):

- SpO₂ ≤93% from any source
- Heart rate ≥125 beats/minute
- Respiratory Rate ≥30 breaths/minute
- Medical Attended/MA-COV

In addition, a moderate case identified by the algorithm that resulted in hospitalization will be sent for adjudication.

For all other cases identified by the algorithm as moderate (tier III if 3 or more signs/symptoms, tier IV if <3 signs/symptoms)^b, adjudication may be performed for only a proportion of such cases, i.e. a sample approach. That is, the CSAC will be presented with the programmed algorithm outcomes and be asked to review a sample of such cases. Based on the results of these “sample adjudications”, the CSAC will make a recommendation whether the programmed algorithm can serve as the default method of adjudication for the remainder of such cases.

Participants identified by the algorithm as asymptomatic/ undetected infections based on a PCR positive result during the course of their participation in the study and/or based on having seroconverted during their study time will be sent for adjudication only when the algorithm captures the presence of COVID-19 symptoms at any point up to 7 days prior to the onset of an algorithmic asymptomatic SARS-CoV-2 infection or prior to seroconversion.

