5.2.4.3. Severe/Critical COVID-19 Case Derivation

A case will be considered severe/critical if (black, terminology from the Medically-attended COVID-19 Form (MA-COV) or [blue, terminology from the eCRF](#)):

- Clinical signs at rest indicative of severe systemic illness (respiratory rate ≥ 30 breaths/minute, heart rate ≥ 125 beats/minute, oxygen saturation (SpO_2) $\leq 93\%$ on room air at sea level, or partial pressure of oxygen/fraction of inspired oxygen ($\text{PaO}_2/\text{FiO}_2$) <300 mmHg)
- Respiratory failure (defined as needing high-flow oxygen, non-invasive ventilation, mechanical ventilation, or extracorporeal membrane oxygenation [ECMO])
- Shock (defined as systolic blood pressure <90 mmHg, diastolic blood pressure <60 mmHg, or requiring vasopressors)
- Significant acute renal or hepatic dysfunction
- Numbness, tingling, or weakness face or limbs (neurologic dysfunction)
- Difficulty speaking or forming speech (neurologic dysfunction)
- Difficulty understanding speech (neurologic dysfunction)
- Feelings of confusion (neurologic dysfunction)
- [Admission to the ICU \(Medical Encounters eCRF\)](#)
- [Death \(SAE form\)](#)

In addition, severe/critical cases can be identified through the use of the following vital signs:

- [SpO₂ ≤ 93%](#)
- [Heart rate ≥125 beats/minute](#)
- [Respiratory Rate ≥30 breaths/minute](#)

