6.6. Appendix 6 FDA Toxicity Grading Scale for Vaccine Trials

Adapted from the FDA Guidance document “Toxicity Grading Scale for Healthy Adult and Adolescent Volunteers Enrolled in Preventive Vaccine Clinical Trials” (September 2007)

Local Reaction to Injectable Product	Mild (Grade 1)	Moderate (Grade 2)	Severe (Grade 3)	Potentially Life Threatening (Grade 4)
Pain/Tenderness [#]	Aware of symptoms but easily tolerated; Does not interfere with activity; Discomfort only to touch	Notable symptoms; Requires modification in activity or use of medications; Discomfort with movement	Incapacitating symptoms; Inability to do work, school, or usual activities; Use of narcotic pain reliever	Hospitalization; Pain/tenderness causing inability to perform basic self-care function
Erythema [#]	25 – 50 mm	51 – 100 mm	>100 mm	Hospitalization; Necrosis or exfoliative dermatitis
Swelling [#]	25 – 50 mm	51 – 100 mm	>100 mm	Hospitalization; Necrosis

[#] Revised by the sponsor.

Vital Signs *	Mild (Grade 1)	Moderate (Grade 2)	Severe (Grade 3)	Potentially Life Threatening (Grade 4)
Fever (°C) ** (°F)**	38.0 - 38.4 100.4 - 101.1	38.5 - 38.9 101.2 - 102.0	39.0 - 40.0 102.1 - 104.0	>40 >104.0
Tachycardia - beats per minute	101 – 115	116 – 130	>130	Hospitalization for arrhythmia [#]
Bradycardia - beats per minute***	50 – 54	45 – 49	<45	Hospitalization for arrhythmia [#]
Hypertension (systolic) - mm Hg	141 – 150	151 – 155	>155	Hospitalization for malignant hypertension [#]
Hypertension (diastolic) - mm Hg	91 – 95	96 – 100	>100	Hospitalization for malignant hypertension [#]
Hypotension (systolic) – mm Hg	85 – 89	80 – 84	<80	Hospitalization for hypotensive shock [#]
Respiratory Rate – breaths per minute	17 – 20	21 – 25	>25	Intubation

* Participant should be at rest for all vital sign measurements.

** For oral temperature: no recent hot or cold beverages or smoking.

*** When resting heart rate is between 60 – 100 beats per minute. Use clinical judgement when characterizing bradycardia among some healthy participant populations, for example, conditioned athletes.

[#] Revised by the sponsor.

Statistical Analysis Plan VAC31518COV3001

Systemic (General)	Mild (Grade 1)	Moderate (Grade 2)	Severe (Grade 3)	Potentially Life Threatening (Grade 4)
Vomiting [#]	No interference with activity or 1 – 2 episodes/24 hours	Some interference with activity or >2 episodes/24 hours	Prevents daily activity, requires outpatient IV hydration	Hospitalization; Hypotensive shock

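### Daily-maximum rule for vital signs in COVID-19 episodes reports the best oxygen saturation of the day and the blood pressure furthest from hypotension

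*SAP*

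**What the plan says.** The COVID-19 paragraph of SAP Section 5.7.2 covers temperature, blood pressure (systolic and diastolic), heart and respiratory rates and the two oxygen measures. For the whole list it sets this output: "oxygen saturation, and pulse oximetry, values and the percentage of participants with values beyond clinically relevant limits will be summarized at each scheduled time point". The same paragraph then fixes how the schedule for COVID-19 cases is built. It starts on Day 1 of the episode and "will be on a daily basis and take the maximum of the values recorded for each subject per day". No parameter is exempted, and no minimum appears anywhere in the section.

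Elsewhere the SAP treats low values of two of these signs as adverse. Section 5.2.4.3 makes SpO2 at or below 93% a criterion for severe/critical disease, and also "Shock (defined as systolic blood pressure <90 mmHg, diastolic blood pressure <60 mmHg, or requiring vasopressors". Section 5.2.1 sends a moderate case to adjudication on "SpO₂ ≤93% from any source". Section 5.2.3 counts a sign as present if it occurs at any time in the episode.

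Section 5.7.2 has a second route to abnormal values: "Vital sign abnormalities emerging after double-blind vaccination may be tabulated/listed by worst abnormality grade", using the Appendix 6 grades. This is optional.

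**The concern.** One extreme is applied to signs whose adverse directions differ. A programmer following the sentence would carry the highest SpO2 of each day into the table and would count a participant-day as beyond a lower limit only if every reading that day was low. One normal reading cancels any number of low ones.

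At stake is the descriptive account of oxygen saturation and blood pressure over the episode. It would understate desaturation and low blood pressure. It could also show a participant within limits on the very day whose reading made the case severe/critical, so two outputs of the same report would disagree.

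**Working it through.** The SAP states no figure on this point, so there is none to reproduce. The check is one of direction, followed by an illustration of size.

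**Direction.** Inputs from the SAP: the daily maximum (Section 5.7.2); the lower limits SpO2 ≤93%, systolic <90 and diastolic <60 mmHg (Section 5.2.4.3). Section 5.7.2 does not define its clinically relevant limits; I take the severity limits as the natural candidates. For readings x1,…,xk on one day and a lower limit c:

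- the maximum is at or below c only if all k readings are;
- the minimum is at or below c if any one reading is.

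Two invented days show the effect:

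- SpO2 of 91, 95 and 96%: the maximum is 96, not counted; the minimum is 91, counted.
- Systolic pressure of 86, 98 and 112 mmHg: the maximum is 112, not counted; the minimum is 86, counted.

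With k = 1 the two rules agree.

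**Size, first model.** Assumptions, none from the SAP: readings are normal around a day mean with within-day SD 1.5 points, independent given that mean, and rounded to 1%. A reading is then ≤93 with probability p = Φ((93.5 − mean)/1.5). The chance of any low reading is 1 − (1 − p)^k, and of all readings low p^k.

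| Day mean | p | k | Any reading low | All low (counted by maximum) |
|---|---|---|---|---|
| 93% | Φ(0.333) = 0.631 | 2 | 1 − 0.369² = 0.86 | 0.631² = 0.40 |
| 93% | 0.631 | 3 | 1 − 0.369³ = 0.95 | 0.631³ = 0.25 |
| 92% | Φ(1.0) = 0.841 | 3 | 1 − 0.159³ = 0.996 | 0.841³ = 0.595 |
| 90% | Φ(2.333) = 0.990 | 3 | about 1.00 | 0.990³ = 0.97 |
| 95% | Φ(−1.0) = 0.159 | 3 | 1 − 0.841³ = 0.40 | 0.159³ = 0.004 |

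The gap is wide near the limit and almost closes when saturation is low throughout the day.

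**Size, second model.** Here p is set directly from 0.1 to 0.7, with k = 2 to 4 fully independent readings. The share of any-low days that the maximum misses is 1 − p^k / [1 − (1 − p)^k].

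- Smallest in the grid, p = 0.7 and k = 2: 1 − 0.49/0.91 = 0.46.
- Middle, p = 0.5 and k = 3: 1 − 0.125/0.875 = 0.86.
- Largest, p = 0.1 and k = 4: 1 − 0.0001/0.3439, close to 1.

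**Is another output a substitute?** The Appendix 6 vital-signs table has a row for "Hypotension (systolic) – mm Hg" but none for oxygen saturation or low diastolic pressure. Neither the optional worst-grade table nor the listing of abnormalities of at least grade 3 in Section 5.7.2, both of which rest on grades, replaces this summary for those two signs.

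**The case against.** The strongest reply is that little rests on this table. A low reading still reaches the analyses that matter. It classifies the case as severe/critical (Section 5.2.4.3), at any time in the episode (Section 5.2.3), and flags an otherwise moderate case for adjudication (Section 5.2.1). Section 5.5.4.1 tabulates the adjudicators' reasons for severe disease, and Section 5.7 plans no formal testing of safety data. All of this stands. A reader might infer from the rule that hypoxia is hidden from the trial. The documents do not support that.

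A reader might also infer that the vaccine–placebo contrast in these signs shrinks, because sicker placebo cases are measured more often. Nothing in the SAP shows that measurement frequency differs by arm, so this is conjecture.

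The blood-pressure part is weaker than the SpO2 part. Appendix 6 also grades hypertension, for which the maximum is the right extreme. Section 5.7.2 separates participant and site measurements only for temperature and oxygen saturation, which suggests that blood pressure comes mainly from site contacts, perhaps once a day. The listing of abnormalities of at least grade 3, for vital signs taken at the investigator's discretion, could also still show marked systolic hypotension. This reduces the blood-pressure point but does not remove it.

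The sizes depend on assumed readings near the limit; with a day mean of 90% the maximum still counts about 97% of days. The separate participant and site summaries for SpO2 may also lower the number of readings per source. Both are fair.

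Finally, the sentence might be meant for temperature alone. It does not say so and it follows the seven-parameter list, whereas Section 5.8.1 names temperature when it takes a daily maximum. If that was the intention, the text still needs correcting.

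**Conclusion.** The rule is wrong as written for oxygen saturation and pulse oximetry, and for blood pressure judged against low limits. This follows from what a maximum is, together with the SAP's own lower limits.

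The consequence is confined to the descriptive COVID-19 vital-signs summary of Section 5.7.2, and within it to days with more than one reading. There the table can understate desaturation and low blood pressure and disagree with the case classification. Efficacy endpoints, adjudication and harm monitoring do not use the rule.

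The size cannot be fixed from the SAP, which does not give the number of readings per day. Under the assumed models, the maximum counts 25% of participant-days against 95% with any low reading (mean 93%, three readings), or 97% against about 100% (mean 90%). With 2 to 4 independent readings and p from 0.1 to 0.7 it misses from 46% to nearly all of them. Agreement among readings on the same day, beyond what a shared mean gives, would narrow the gap.

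**What to change.** Replace the sentence in Section 5.7.2 with the worst daily value in the adverse direction:

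- daily minimum for oxygen saturation and pulse oximetry;
- daily maximum for temperature, heart rate and respiratory rate;
- both minimum and maximum for blood pressure.

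Count a participant-day as beyond limits if any reading that day is beyond them.

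The cost is one sentence and a programming change, with no new data. There is a small statistical price: flagging on any reading rises with the number of readings. In the first model, a day mean of 95% gives 16% of days flagged with one reading and 40% with three. The table should therefore show the number of readings per day by arm, so that a difference in measurement frequency is visible.
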